 - i. Participants will begin MBSR/HP activities within one month of baseline assessment, dependent on the time of their baseline assessment within recruitment schedule
 - ii. Both groups (MBSR and HP) will consist of nine sessions, each approximately 2 hours in length.
 - b. Immediate follow-up
 - i. After the 9th session, participants will complete a questionnaire via tablet that will assess PTSD (primary outcome), secondary outcomes (e.g., depression, substance use), and traumatic events that occurred since first assessment, as well as key covariates (e.g., fidelity to intervention) and additional outcomes (e.g., mindfulness, emotion regulation).
 - ii. Women will provide urine for drug test and repeat the Trauma Imagery Stress Task, providing saliva samples before and after the task.
 - c. 6-month follow-up
 - i. Primary and secondary outcomes and covariates (e.g., fidelity to intervention) will be reassessed via tablet
 - ii. Women will provide urine for a drug test and repeat the Trauma Imagery Stress Task, providing saliva samples before and after the stress task.

3. Phase II Reimbursement

d. Women will receive \$15 for the baseline assessment, \$10 per MBSR/HP session, \$15 for completing the post-intervention assessment, and \$30 for the 6-month follow-up assessment.

i. Women are paid in cash and must sign on the iPad (via REDCap) that they have received the payment. This must also be initialed, signed, and dated by the RA in charge of payment.

Subsection 2.3 - Phase II Recruitment & Treatment Overview

Table 4: Overview of Phase II: Timeline of Mindfulness Trial Procedures & Assessments													
PRE-ASES	SESSMENTS		MBSR or HP Cont	trol	POST-ASSESSMENTS					POST-ASSESSMENTS			
Baseline			Sessions 1-8	Session 9 6-months post-interve			tervention						
Eligibility	Psychosocial	Trauma	Groups meet	Final	Psychosocial	Trauma	Psychosocial	Trauma					
Screen	Questionnaire ^{,a,b}	Imagery	once per week	intervention	Questionnaire b,c	Imagery	Questionnaire b,c	Imagery Task					
PTSD dx		Task		session	PTSD dx	Task	PTSD dx						

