Saliva Sample: The saliva sample is collected to determine resting cortisol, cortisol reactivity, and C-RP (a marker of inflammation). All saliva will be assayed in duplicate using standard manufacturer's protocol (Salimetrics). The concentration of CRP in saliva will be determined using a Salivary C-Reactive Protein ELISA kit, an enzyme-linked immunoassay. The standard curve is run on every assay plate and must have an R2 value of > 0.99. The replicates must have a %CV < 15 or an absolute difference <0.030 between the replicates. The mean values across saliva duplicates will be computed for each sample and used in the statistical analyses.

Subsection 2.12 - Phase II MBSR-based Intervention

Standard MBSR is an eight-week long mindfulness-based intervention (MBI) with one 1.5-2.5 hour session per week (the seventh week has two sessions as one is a mini-retreat). The intervention will be run by a highly experienced instructor with prior experience conducting MBSR with individuals exposed to trauma with PTSD.

During MBSR, participants are trained in mindfulness meditation and the applicability of mindfulness to daily life. During MBSR programing, teachers will lecture about key topics in mindfulness and lead class discussions. Participants are given opportunities to ask the instructor questions and to share their experiences with each other. Snacks and drinks will be provided. Important to note, the intervention in this study is not true MBSR. It has been modified to fit the specific needs of the target population. This includes shorter sessions and shorter meditations, and additional flexibility on the part of the trainer. Although many of the same tools and procedures in traditional MBSR will be utilized, given these critical differences the intervention administered in this study is *not* true MBSR.

Each week in the MBSR program focuses on a different theme and has specific short homework assignments that students are asked to complete. The sessions are as follows:

- Week 1: Introductory Material. This includes an overview of the course, building trust within the group, introduction to mindful eating, some standing yoga stretches, mindful breathing and body scan meditation

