Mindful awareness attention scale (MAAS): is a 15-item scale designed to assess a core characteristic of mindfulness, namely, a receptive state of mind in which attention, informed by a sensitive awareness of what is occurring in the present, simply observes what is taking place (Brown & Ryan, 2003; Carlson & Brown, 2005).

Five facet Mindfulness Questionnaire (FFMQ) is a 39 item questionnaire that assesses five independent sub-scales: observing, describing, acting with awareness, non-judging of inner experience, and non-reactivity to inner experience (Baer et al., 2008).

Life event history: Life events history will be assessed by asking respondents whether they ever experienced each of 40 specific negative life events (NLEs; will include both trauma and stressors), and, if so, at what age(s) this occurred. This will also be updated with respect to recent events upon immediate completion of the 9 week courses as well as at the 6-month follow up. The measure was modified from the Diagnostic Interview Schedule trauma section (Robins, Helzer,

Croughan, & Ratcliff, 1981) by including several stressful or traumatic events reported by primary care patients ([name], Silver, & Waitzkin, 2000) and has provided rates of events comparable to other community-based studies (e.g., Seery et al., 2010).

Emotion regulation: will be assessed with the Difficulties in Emotion-Regulation Scale (DERS; Gratz & Roemer, 2004; Kaufman et al., 2016), short form. DERS is a 18- item questionnaire that aims to measure how much one is able to regulate/deregulate their emotions. The 41 questions are based off of six factors including acceptance of emotions, impulsiveness, ability to work towards goals, awareness of own emotions, clarity of emotions, and accessibility to emotion-regulation strategies

Social support will be assessed using the MOS Social Support scale (Sherbourne & Stewart, 1993) This 19 item measure assesses social support.

Anxiety: will be assessed using the PROMIS measure for anxiety (Emotional Distress). The 8-tem form will be used. It assesses symptoms of Generalized Anxiety Disorder. it is desirable to use the 8-item short form, which has reliability and validity comparable to the 28-item computer adaptive form (PROMIS Health Organization, 2019).

General Self-efficacy scale: This 10-item scale was created to assess a general sense of perceived self-efficacy (Schwarzer & Jerusalem, 1995).

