Demographics: Age, ethnicity, sexual orientation, incarceration history, religion, income, education, number of children, pregnancy status, mental health history (previous diagnosis) employment history.

Prior Doctor-diagnosed Health Conditions. This survey, modified from the CDC's National Center for Health Statistics Annual National Health Interview Survey, asks respondents to report doctor diagnosed health ailments. This will be assessed at baseline, immediately following 9th/final intervention session, and 6-month follow-up.

Adherence. Measured by class attendance and self-reported time in mindfulness meditation and doing at-home assignment.

Short self-compassion scale. This 12-item scale assesses self-compassion (Raes, Pommier, Neff, & Van Gucht, 2011).

Free Response: Participants will be given the opportunity to provide written feedback regarding their experiences that may not have been captured with these quantitative measures. Prompt will include: We will ask: "Do you have any other thoughts and/or feelings about your participation in this program? Is there anything that you wish to share with us regarding your experience?"

Collection Procedure*

*Please keep a roster of all samples collected from October 2019 onwards. Samples may contain SARS- CoV-2, and this will ensure safe handling in the future as labs may take extra precautions when handling samples collected during this time.

- 1. Participants wash hands for 20 seconds prior to collecting the saliva sample(s).
- 2. Collect saliva sample as normal (follow typical passive drool or swab collection protocols). Tubes should be labeled prior to providing them to participants.
- Sample tubes should be immediately capped and sealed. Outsides of tubes should be disinfected following collection. Disinfectants are listed on the CDC website (https://www.epa.gov/pesticide-registration/list-n-disinfectants-use-against-sars-cov-2). Ensure no disinfectants leak into the tube via an unsealed or partially sealed tube.
- 4. Samples should be placed in a secondary container (sealed plastic bag with absorbent material, freezer box, etc.) that is labeled, then placed in a freezer (-20°C) as soon as possible. See below for more guidelines.
- 5. Participants should wash hands for at least 20 seconds after collecting the saliva sample(s).

Sample Storage and Shipping

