All analyses were conducted using STATA 18. First, descriptive statistics were calculated for the total sample. Next, a series of multilevel models were conducted for each primary and secondary outcomes using a multilevel, random-intercept mixed. Participants were entered as random effects to nest observations within participants, allowing for correlations within each individual over time. Group assignment (i.e., MBSR vs. HP Control), time (i.e., T1, T2, and T3), and group-by-time interactions were entered as fixed effects. Site was also included as a fixed-effect, given the low number (i.e., two) of sites¹. Covariates were screened for inclusion in bivariate analyses and included if statistically significant and theoretically meaningful. An independent covariance pattern was specified as our final models were random-intercept (nested within participant) only². Results are presented using restricted maximum likelihood for optimal control of Type 1 error³. An intention-to-treat analysis was conducted, where every participant was included in the final analyses, regardless of whether they completed all of the sessions.

Bibliography

- 2. Weise RE. *Modeling Longitudinal Data*. 1st ed. Springer; 2005.
- 3. Luke SG. Evaluating significance in linear mixed-effects models in R. *Behav Res Methods*. 2017;49(4):1494-1502. doi:10.3758/s13428-016-0809-y

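### The SAP's covariate screening is not limited to pre-intervention variables, so fidelity, the protocol's only named covariate example, can enter a model labelled intention-to-treat

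*Combined protocol and SAP*

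**What the plan says.** The Statistical Analysis Plan fits a random-intercept model to each primary and secondary outcome. Its fixed terms are: "Group assignment (i.e., MBSR vs. HP Control), time (i.e., T1, T2, and T3), and group-by-time interactions were entered as fixed effects". Site is a further fixed effect. Beyond these, "Covariates were screened for inclusion in bivariate analyses and included if statistically significant and theoretically meaningful". No candidate list, significance threshold or limit on when a covariate is measured is given. The same paragraph calls the analysis intention-to-treat, defined by who is included: "where every participant was included in the final analyses, regardless of whether they completed all of the sessions".

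Outside the SAP, the protocol speaks of covariates in two places, both in Section 2.2, item 2, and both times with the same example. At the immediate follow-up the questionnaire covers outcomes "as well as key covariates (e.g., fidelity to intervention) and additional outcomes (e.g., mindfulness, emotion regulation". At 6 months, "Primary and secondary outcomes and covariates (e.g., fidelity to intervention) will be reassessed via tablet".

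Table 4 (Section 2.3) pairs fidelity with adherence. Appendix IV defines adherence as "Measured by class attendance and self-reported time in mindfulness meditation and doing at-home assignment". On the MBSR arm, Section 2.12 says: "Each week in the MBSR program focuses on a different theme and has specific short homework assignments that students are asked to complete". Section 2.13 lists the nine Health Promotion sessions and mentions no homework.

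**The concern.** An intention-to-treat contrast compares women by assigned arm. Including every woman is necessary for that, but not sufficient: the model must also not adjust away, or distort, the difference by conditioning on something the assignment has changed. Fidelity is such a variable. It cannot exist before session 1, and part of it, meditation and home-assignment time, is likely to be larger in the arm that is given meditation homework.

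The SAP's two filters do not address this. Statistical significance tests association with the outcome, and theoretical relevance tests plausibility; neither tests timing. A variable that the protocol itself calls a key covariate would plausibly pass the second.

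At stake is the interpretation of the main result. A reader of the SAP cannot tell whether the reported group-by-time estimate is the effect of being assigned to MBSR or that effect net of practice.

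**Working it through.** **1. Plan's own figure.** None exists to reproduce. The documents state no effect size, SD, alpha or power, so the size below is conditional on assumptions and is given in outcome SD units.

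**2. Timing.** Fidelity is named at the post-session-9 and 6-month assessments (Section 2.2) and is absent from the baseline battery in Section 2.8. As collected, it is a repeated T2/T3 measure.

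**3. Algebra.** Let tau be the effect of assignment at T2, P the practice or fidelity score (within-arm SD 1, 0 at T1), g the difference in mean P between arms, and s the within-arm slope of post-intervention outcome on P. The post-intervention part of the outcome is

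tau × arm + s × (P − g × arm) = (tau − s × g) × arm + s × P.

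With P in the model as a time-varying term, the group-by-time coefficient therefore estimates tau − s × g. The shift is −s × g, which is zero when g = 0.

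Worked case: tau = −0.40, s = −0.2, g = 1 gives −0.40 − (−0.2 × 1) = −0.20.

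**4. Simulation check.** Random-intercept REML, 2,000 runs per scenario, 67 women per arm (Section 2.5), T1 only / T1–T2 / all three = 7/12/48 per arm (from the 134, 120 and 96 in Section 2.16), unit SD, within-woman correlation 0.5, no class clustering. T2 group-by-time estimate for a true −0.40, with simulated values and the algebraic value in brackets:

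| Arm gap g | s = −0.1 | s = −0.2 | s = −0.3 |
|---|---|---|---|
| 0.5 | −0.348 (−0.35) | −0.301 (−0.30) | −0.256 (−0.25) |
| 1 | −0.298 (−0.30) | −0.197 (−0.20) | −0.094 (−0.10) |
| 2 | −0.199 (−0.20) | −0.004 (0.00) | +0.196 (+0.20) |

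Without the covariate, all nine cells gave −0.396 to −0.406. A practice-by-time term gave results within 0.006 of those shown. At g = 1, rejection was 0.575–0.596 without the term and 0.340/0.172/0.075 with it.

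- **Direction.** With s = +0.1 and g = 1 the estimate is −0.497 (algebra −0.50), so the shift can also exaggerate benefit.
- **No mediation needed.** Take tau = 0 and s = −0.2 arising only from a shared cause of practising and recovering. At g = 0.5/1/2 the estimate is +0.106/+0.199/+0.401, with rejection 0.096/0.182/0.422 against 0.055–0.064 without the term. These rates hold given that the term has entered.

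**5. Second simulation, different set-up.** Known variance components, no dropout, 1,500 runs. Fidelity is correlated 0.5 with an unmeasured tendency to improve that carries −0.3 per SD, so s = 0.5 × (−0.3) = −0.15. The predicted shift is 0 at gap 0, +0.075 at gap 0.5 and +0.15 at gap 1. A true −0.40 was estimated as −0.396, −0.327 and −0.248; a true 0 as +0.002, +0.082 and +0.152.

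**6. Harmless forms.** In the step 4 simulation, one constant practice value per woman changed the contrast by 0.002–0.005 on average in absolute size. A baseline covariate correlated 0.22 with the outcome changed it by 0.005. The SE was 0.180–0.185 with or without that baseline covariate.

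**The case against.** The protocol's mention of fidelity is an example in a data-collection list, not a model specification, and no section says that it was entered. Only some forms of entry matter. A constant value per woman, such as the class count kept in the REDCap tracker (Section 2.16), is harmless. A covariate-by-time term is not among the interactions the SAP lists. Leaving fidelity blank at T1 could not yield the T1-referenced contrasts that the SAP describes. What remains is a T1 value filled in by the analyst and a time-varying term, which no section describes. Every slope and gap above is assumed.

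Most of this stands, and it limits the point to what the rule permits. It does not remove it: a variable recorded at T2 and again at T3 is most naturally stored as time-varying, and the rule as written would accept it.

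Three stronger readings are tempting but unsupported:

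- **That the reported results are already biased by fidelity.** The documents do not show that it entered.
- **That any variable re-measured after the intervention starts does the same harm.** Appendix IV says of life events, "This will also be updated with respect to recent events upon immediate completion of the 9 week courses", but a shift requires an arm difference, and the documents give no reason to expect one there.
- **That the screen would probably select fidelity.** Any such probability follows from the assumed slope, gap and threshold, none of which the documents state.

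**Conclusion.** The point holds in conditional form and should be fixed. The screening rule sets no timing limit, and the protocol's only covariate example is a post-assignment variable with an arm-specific component, so following the plan as written can produce a model that does not estimate the effect of assignment.

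The size is −s × g. It reaches half of an assumed −0.40 SD effect at s = −0.2 and g = 1 SD, and is nil at g = 0. It arises only if fidelity enters in time-varying or time-interacted form and differs between arms. That the arms differ is a reasonable inference from homework being described only for MBSR, but the amount is unknown. The calculations show that harm is possible, not that it occurred. Selection among baseline or time-constant covariates is a minor matter for this contrast.

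**What to change.** Replace the screening sentence in the SAP with:

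> The primary model for every outcome contains group, time, group-by-time and site; any further covariate is a named pre-intervention variable, the same across outcomes. Fidelity, attendance, home practice and other variables measured after the intervention starts are not entered in the intention-to-treat models and are used only in a separate adherence or mediation analysis.

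The SAP is written in the past tense and reports completed models. For each outcome, state which covariates were screened and which entered, when each was measured and in what form. Refit without any post-intervention covariate that entered. Where only baseline covariates entered, refitting is not required.

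The cost is at most a minor reanalysis of data already held. It needs no new data and keeps the SAP's group, time and site structure.

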In Phase II, we will assess the potential benefit of MBSR to reduce PTSD (primary outcomes) and secondary outcomes (e.g., depression, SUD, CRP, cortisol reactivity), among 130 eligible homeless women who exhibit likely subthreshold or threshold PTSD living at one of two residential drug treatment facilities. MBSR will be compared to an attention-control group (Health Promotion Wellness Classes; HP). There originally intended to be five cohorts of women, each with 12-15 women (total of 24-30 women per cohort). However, due to COVID-19 adjustments have been made in terms of the class size and randomization procedure. At each cohort, sites will be randomized to receive either the MBSR or the HP. Although sites will alternate between MBSR and HP by cohort, each participant will receive either the MBSR or the HP. Randomization will occur using RedCAP. The women participate in either MBSR or HP for 9 weeks. Psychosocial data will be collected at baseline, immediately following final intervention session, and at 6-month follow-up via tablet questionnaires. After psychosocial data collection, a stress task (Trauma Imagery Task) will be conducted at each time point, with saliva collected both before and after the task to assay cortisol and CRP. This proposal will improve on the methodological rigor of prior research on MBIs for PTSD in disadvantaged populations by using: randomization procedures that account for cross-contamination; blind evaluators; longitudinal follow-up; an attention control group equal to the MBI intervention in both contact visits and hours; increased demographic diversity; comprehensive lifetime trauma assessment; and inclusion of objective indices of stress responses to accurately evaluate the effectiveness of MBIs in treating trauma-related symptoms.

Confidentiality and Ethical Issues

All program staff must follow confidentiality and ethical procedures throughout this program to ensure that everybody is treated with respect and dignity.

1. Communication with study participants must remain confidential. To maintain confidentiality for participants, any personal information provided, such as participants' name, age, etc., will

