The RA will read the consent to screen script on REDCap. Potential participants are free to stop at any time – remind them that all procedures are completely voluntary. [name] and/or someone from the Lab Management team will always be onsite to help answer questions.

Participants will then be given an eligibility screener via tablet with either [name] or a trained research assistant available to answer any questions. The screener will first assess for age, prior homelessness, and cognitive competence. The screener then screens for PTSD using the PTSD Checklist for DSM-5 (PCL-5) for *the worst event in their life*. We will assess PTSD to their most recent event (in the past year) during the baseline and follow-up assessments. The standard PCL-5 initially starts with the identification of the presence of exposure to a DSM-5 traumatic event and then assesses whether it involved actual or threatened death, serious injury or sexual violence. The RA may need to prompt the potential participant with examples to keep them on track and to ensure that the participant is responding to an actual DSM-5 traumatic event. The next 20 items on the PCL-5 assess all four B-E PTSD criterion (re-experiencing, avoidance, negative thoughts or cognitions, hyperarousal), assessed on a Likert-type scale 0 "not at all", 1 "a little bit", 2 "moderately", 3 "quite a bit", 4 "extremely". Subthreshold PTSD will be defined as endorsing "moderately" or more to at least 2 B-E criteria; probable-PTSD will be measured by meeting criteria A-G for PTSD.

Data collection method: All data will be collected via encrypted tablets will be programmed by the Research Director from the School of Nursing and responses will be automatically, electronically scored. Data is not stored on the tablets. It is automatically transferred to the All participants who complete the screener will receive \$3.

Subsection 2.5 - Phase II Eligibility Criteria

Inclusion Criteria:

- 1) Homeless women (N=134; 67 in each group)
 - a. Women over 18 years of age
 - b. Able to speak English
 - c. Homeless in the last 6 months: a homeless person is defined as anyone who spent the previous night in a public or private shelter, or on the street.
 - d. Lifetime exposure to trauma as defined by the Diagnostic and Statistical Manual for Mental Disorders, 5th Edition (DSM-5).
 - e. Likely subthreshold or threshold PTSD, as measured by the PCL-5.

Exclusion Criteria:

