The following will **not** be eligible for participating:

- 1) Persons who are:
 - a. Not able to speak English
 - Judged to be cognitively impaired, as indicated by score > 10 on the Short-Blessed Screener

Subsection 2.6 - Phase II Laboratory Tests/Sample Collection

Saliva Sampling and Results

Saliva Collection

- Pre-task, saliva will be collected. All saliva collection will occur between 10am-2pm to minimize diurnal fluctuation effects. (Study procedures may start before 10, but first saliva sample must be collected after 10:00am; the second sample must be collected before 2pm participants must be scheduled according to these specifications).
- Two whole saliva samples will be collected using an unstimulated passive drool technique.
- Women will be instructed to avoid eating, brushing teeth, or smoking for one hour prior to the assessment and will be asked to wait to begin the task if they have.
- Participants will rinse their mouths thoroughly with water for 10 minutes before samples are collected. Participants will then passively drool into a collection vial for three minutes or until 0.80 milliliters of fluid is collected.
- Saliva samples will be immediately placed in the on-site freezer (or ice cooler) and be taken to IISBR within 36 hours to be frozen at -80°C until assayed.
- All samples will be assayed for salivary cortisol and CRP using a highly sensitive enzyme immunoassay (Salimetrics, IISBR).
- **Twenty minutes after task completion**, saliva samples will be collected again in an identical manner to that described above.
- Participants will then be offered snacks and a drink and be debriefed to ensure they are not experiencing severe task-related psychological distress. In the unlikely event of participant distress, an immediate referral will be made to on-site professional staff.

Subsection 2.7 - Phase II Intervention Program Description

General Description: Among 134 eligible trauma-exposed homeless women, assess the impact of the MBSR intervention program PTSD symptoms (primary outcomes), and substance abuse, depression, cortisol reactivity, and inflammation (secondary outcomes).

Data Collection Time points: Baseline, 2 months, and 6 months

Total Duration: 6 months

The following sections will outline the intervention process:

- Pre-intervention Assessments
- Brief Stress Task (Trauma Imagery Stress Task)
- Biospecimen Collection
- Biospecimen Analysis
- MBSR Intervention
- Health Promotion Intervention
- Post-Assessment

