Participants have the right to refuse the collection of urine or saliva and it is important to understand that an individual may want to refuse due to the following:

Step 1: Assess reasons why participant does not want to have their sample collected.

- May experience concern that their friends, acquaintances, or shelter staff will be informed of the results of their surveys or urine.
- Other possible reasons?

In the event a participant refuses the sample collection, inquire about the following:

Step 2: Respond to their reasons why they do not want to give urine or saliva samples.

We encourage our participants to complete as many of the procedures as they are comfortable with. Please offer to have [name] or Lab Management answer any questions the participant may have regarding the measures. However, participation is completely voluntary, and the participant may skip any aspect of the procedure that they chose without penalty and still be in the study.

Subsection 2.16 - Phase II Dealing with Intervention Program Attrition

Attrition is conservatively estimated at 10% for first follow-up and 20% for 6 month follow-up. To account for an estimated 30% of women to be screened with subthreshold or threshold PTSD, 448 women will be screened, approximately 134 enrolled, with approximately 120 for immediate post-intervention assessment and 96 at 6-month follow-up. This may change due to COVID-19, but we will work hard to ensure retention of participants during the study. The Locator Guide is key to maintaining effective follow-up.

• Completion of the intervention program is defined by completing at least 6 out of the 9 classes. We will keep track of the number of classes using the adherence tracker on REDCap. Make-up classes will be offered to women who can not make the class,

particularly as it pertains to COVID-19 or other obligations the women have such as court appearances.

• The minimum amount of time required for the regimen is 8 weeks and the maximum is 10 weeks.

Subsection 2.17 - Phase II Follow-Up Focus Groups

At six-month follow-up, we will contact the women with assistance from the site supervisor or by using our Locator Guide (see Appendix). Research Staff will travel to the participant's location, as they may not be available to return to site due to COVID-19 restrictions or other factors. If participant moved out of state, the follow-ups may be conducted over Zoom or phone.

Subsection 2.18 - Phase II Compensation

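### The random-intercept-only model forces one variance and one correlation on three unequally spaced waves; if that is wrong, the group-by-time tests are mis-sized in a direction the documents do not determine

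*Combined protocol and SAP*

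**What the plan says.** The Statistical Analysis Plan describes a mixed model for each outcome, with a random effect for participant that is meant to account for repeated measures, "allowing for correlations within each individual over time". The fixed part is given as "Group assignment (i.e., MBSR vs. HP Control), time (i.e., T1, T2, and T3), and group-by-time interactions were entered as fixed effects", plus site. On the covariance it says: "An independent covariance pattern was specified as our final models were random-intercept (nested within participant) only". On estimation it says: "Results are presented using restricted maximum likelihood for optimal control of Type 1 error".

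It names no other residual structure, robust standard error, degrees-of-freedom method or sensitivity analysis for the covariance. It does not say which contrast is the primary test, and it states no significance level.

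On timing, Subsection 2.7 of the protocol has "Data Collection Time points: Baseline, 2 months, and 6 months". Subsection 2.1 has "Psychosocial data will be collected at baseline, immediately following final intervention session, and at 6-month follow-up via tablet questionnaires", and Table 4 counts the last wave from the end of the intervention. The waves therefore fall at about 0, 2 and 6 months or about 0, 2 and 8 months. The spacing is unequal on either reading.

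**The concern.** With a single random intercept (variance τ²) and independent residuals (variance σ²), every wave has variance τ² + σ² and every pair of waves has correlation τ²/(τ² + σ²). This is compound symmetry. It holds whether the word independent describes the residuals or the random-effects matrix, because with one random effect that matrix has nothing to restrict and no other residual structure is named.

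The protocol gives two reasons to doubt it. The gaps between waves differ, so the pairwise correlations may differ. Enrolment also requires a minimum of PCL-5 symptoms (Subsection 2.5), and the PCL-5 is the primary outcome (Appendix IV), so baseline variance may be smaller than follow-up variance.

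The model applies one averaged within-woman variance to both the T2 and the T3 change contrasts. If the true change variances differ, the standard errors are wrong. REML addresses bias in variance components under the assumed structure. It does not correct the structure, so the assurance about Type 1 error depends on compound symmetry being true. Likelihood-based handling of dropout also relies on the modelled covariance.

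**Working it through.** **Inputs from the documents.** Subsection 2.5 has "Homeless women (N=134; 67 in each group". Subsection 2.16 has "Attrition is conservatively estimated at 10% for first follow-up and 20% for 6 month follow-up" and expects 448 screened, 134 enrolled, 120 at T2 and 96 at T3. That chain reproduces: 448 × 0.30 = 134.4; 134 × 0.90 = 120.6; 120 × 0.80 = 96.0. Per arm this is 67, 60 and 48, and the loss by T3 is 1 − 96/134 = 28%.

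**Assumed, because the documents give no figure.** Two-sided 5% level; all standard deviations and correlations; the class intraclass correlation.

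**Formula (complete data).** Let D2 = Var(T2 − T1), D3 = Var(T3 − T1), D23 = Var(T3 − T2), and A = (D2 + D3 + D23)/3. Under compound symmetry each change contrast uses A in place of its own variance. Hence SE ratio = √(A/D), and actual size = 2·P(Z > 1.96 × SE ratio).

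**Worked case.** SDs 14/17/19; correlations r12 = 0.6, r13 = 0.4, r23 = 0.5.
- D2 = 196 + 289 − 2(0.6)(14)(17) = 199.4
- D3 = 196 + 361 − 2(0.4)(14)(19) = 344.2
- D23 = 289 + 361 − 2(0.5)(17)(19) = 327.0
- A = 290.2
- T2: √(290.2/199.4) = 1.21, size 1.8%
- T3: √(290.2/344.2) = 0.92, size 7.2%

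**Other assumed covariances (complete data, change from baseline).**

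| SDs (T1/T2/T3) | r12, r13, r23 | D2, D3, D23 | Size at T2 | Size at T3 |
|---|---|---|---|---|
| equal | 0.7, 0.343, 0.49 (decay 0.7 per 2 months, T3 at 6 months) | 0.60, 1.314, 1.02 | 1.2% | 9.1% |
| equal | 0.6, 0.5, 0.55 | 0.8, 1.0, 0.9 | 3.8% | 6.3% |
| equal | 0.5, 0.5, 0.5 | 1, 1, 1 | 5.0% | 5.0% |
| equal | 0.5, 0.4, 0.6 | 1.0, 1.2, 0.8 | 5.0% | 7.4% |
| equal | 0.4, 0.4, 0.7 | 1.2, 1.2, 0.6 | 7.4% | 7.4% |
| 0.8/1/1 | 0.5 throughout | 0.84, 0.84, 1.00 | 4.3% | 4.3% |
| 0.8/1/1 | 0.4, 0.4, 0.6 | 1.0, 1.0, 0.8 | 5.8% | 5.8% |
| 1/1.3/1 | 0.5 throughout | 1.39, 1.00, 1.39 | 6.2% | 2.8% |
| 1/1.3/1 | 0.6, 0.45, 0.55 | 1.13, 1.10, 1.26 | 4.7% | 4.4% |

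Across equal-variance decay of 0.5 to 0.7 per 2 months, with T3 at 6 or 8 months, the sizes are 0.7-2.0% at T2 and 7.6-9.1% at T3 with complete data. With the planned dropout (67/60/48 per arm) they are 0.9-2.3% and 7.8-9.6%.

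**If the test is instead the group difference at a wave.** The complete-data comparison is the average of the three variances against the variance at that wave. Equal variances give exactly 5.0%. Under equal-variance decay with dropout, the sizes are 4.7-4.9% at T2 and 5.2-5.8% at T3. With SDs 0.8/1/1 and correlations 0.5, the average variance is (0.64 + 1 + 1)/3 = 0.88, the ratio is √0.88 = 0.938, and the size is 6.6% at both waves. With SDs 1/1.3/1 the sizes are 9.5% at T2 and 3.0% at T3.

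**If the test is the joint two-degree-of-freedom interaction.** Under equal-variance decay the size is 5.1-6.3%.

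**After the change.** A correct unstructured covariance brings both contrasts to 5% asymptotically. With a plain normal reference the size is 5.2% at 67 per arm (t with 132 df) and 5.3% at 48 per arm (t with 94 df).

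**What remains.** Whole classes are allocated. Class size is 134/10 = 13.4 with five cohorts, or 134/14 = 9.6 if the seven cohorts on the timeline each have two classes (assumed). With DEFF = 1 + (m − 1) × ICC and size = 2·P(Z > 1.96/√DEFF), an ICC in the tested contrast of 0.01, 0.02 or 0.05 gives 6.0-6.5%, 7.0-7.9% or 10.1-12.4%.

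**The case against.** A reader might infer that the T2 test is conservative and the T3 test anti-conservative as a matter of fact. The documents do not support this. The pattern appears when r12 is the largest correlation and r13 the smallest, variances are roughly equal, and the test is on change from baseline. None of these is established.

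The protocol also gives reasons to expect otherwise. Selection on baseline PCL-5 tends to lower the correlations of baseline with later waves, and the intervention falls between T1 and T2. Both favour r23 being highest, and then the two tests need not err in opposite directions.

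The mild decay case (0.6, 0.5, 0.55) is close to nominal. An 800-trial simulation with dropout gave 5.4% at T3, against a Monte Carlo standard error of √(0.05 × 0.95/800) = 0.8 points. For the joint test, or for group differences at a wave with equal variances, little inflation remains. The effect on missing-at-random estimation has no size attached. Finally, the plan is written in the past tense, so the change may be a re-analysis after results are known.

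All of this stands as a limit on the claimed direction and size. It does not rescue the model. The alternative tests are not chosen by the plan, and the wave-specific ones are themselves mis-sized when variances differ. Where change contrasts happen to come out near 5% (SDs 1/1.3/1 with decay), the wave-specific tests do not. An unknown direction is a reason not to impose compound symmetry.

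**Conclusion.** The point holds as a specification weakness that is cheap to remedy. The stated model imposes compound symmetry without justification or safeguard, and REML does not secure Type 1 error if that is wrong.

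The size is conditional on assumed covariances. Under equal-variance serial decay the change-from-baseline tests run at about 1-4% at T2 and 6-10% at T3. Across the other patterns tried, the results range from both inflated (7.4%) to both slightly deflated (4.3%), reversed (6.2% and 2.8%) or near nominal. No single direction can be asserted, and the plan does not establish that the T2 or T3 change contrast is the primary test.

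It would also be too strong to infer that an unstructured covariance settles Type 1 error in this trial. It corrects within-woman misspecification only. Clustering by class remains, and at the assumed ICCs it may be the larger inflation.

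**What to change.** Replace the covariance sentence with an unstructured within-woman covariance over T1, T2 and T3 and a small-sample degrees-of-freedom method. In Stata 18: `mixed ... || id:, noconstant residuals(unstructured, t(time)) reml dfmethod(kroger)`. Name the primary contrast: T2 change, T3 change, the joint interaction, or a group difference at a stated wave. Keep the random-intercept model as a sensitivity analysis and report both. If results were already known when the change was made, say so.

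The cost is six covariance parameters instead of two, which about 134 women can support, and a re-run of the models. Drop the claim that REML gives optimal Type 1 error control. Treat class clustering from the site-by-cohort allocation in Subsection 2.1 as a separate item.
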